9.4 Exploratory Efficacy Analysis

Time to blood counts improvement as well as duration of the improvement will be summarized by descriptive statistics (mean, median, and range) and analyzed by Kaplan-Meier (KM) methodology. KM plots will be presented. Median improvement time and median duration of improvement and their corresponding 95% confidence intervals will be provided.

Blood count improvement is defined separately for ANC, platelet count and hemoglobin.

- Improvement of Grade 4 Neutropenia defined as ANC lab values $< 0.5 \times 10^9/L$ lasting for at least 7 days: when ANC lab values improve to $\geq 0.5 \times 10^9/L$ sustaining for a minimum of 5 days.
- Improvement of Grade 4 Thrombocytopenia defined as platelet count lab values $< 25 \times 10^9/L$ lasting for at least 7 days: when platelet count lab values improve to $\geq 25 \times 10^9/L$ sustaining for a minimum of 5 days.
- Improvement of Grade 3 Anemia defined as hemoglobin lab values $< 80 \text{ G/L}$ lasting for at least 7 days: when hemoglobin lab values improve to $\geq 80 \text{ G/L}$ sustaining for a minimum of 5 days.

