### Adverse Events of Special Interest

The following adverse events of special interest will be monitored during the study:

- Cytopenias
- TLS

Subjects will be monitored for blood counts through resolution of cytopenias. Myelosuppression and the related adverse events (thrombocytopenia, anemia, neutropenia, and febrile neutropenia) are common in subjects with AML. Subjects with baseline neutropenia or those with secondary AML might be particularly at high risk for associated adverse events. Additional details are provided in Section 6.2.

If additional dose reductions are thought to be necessary by the investigator, a discussion with the AbbVie medical monitor is required. Subjects experiencing delays for a medical event unrelated to study treatment may delay study treatment up to 4 weeks. Delays greater than 21 days must be discussed with the AbbVie Primary TA MD or a designee.

Anti-infective prophylaxis should be implemented per regional guidelines or institutional standards including appropriate prophylaxis for bacterial, viral, and fungal infections. Potential for drug-drug interactions should be considered and appropriate dose adjustments made if required.

Subjects with resistant disease, based on modified IWG criteria (as described in the Operations Manual, Section 3.16), after End of Cycle 1 will need a bone marrow aspirate to evaluate response after End of Cycle 2. Subjects with resistant disease after end of Cycle 2, based on modified IWG criteria (as described in the Operations Manual, Section 3.16) will need a bone marrow aspirate to evaluate response after end of Cycle 4. Subjects who have not recovered absolute neutrophil count (ANC)  $\geq 500/\mu\text{L}$  within 14 days of drug interruption or require longer duration of interruption between treatment cycles, bone marrow aspirate may be performed, as determined by the investigator, to assess disease status before resuming treatment with next cycle.

Guidelines for TLS management are provided in Section 6.2. Chemistry labs (including creatinine, potassium, calcium, inorganic phosphorus, lactate dehydrogenase, and uric acid) will be performed real-time pre-dose, 4 - 6 hours post-dose, and 24 hours post-dose for each venetoclax dose escalation, and also as deemed necessary per investigator to monitor TLS.

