## Study Activities Table

Activity	Screening	Cycle 1						Cycle 2 Day 1, and Day 1 of every cycle thereafter	Cycles 2 to 6 Days 2 to 7	Cycle 2 Day 28 (only if CR/CRI not achieved at end of Cycle 1)	Cycle 4 Day 28 (only if CR/CRI not achieved at end of Cycle 2)	Final Visit/Cycle 6 Day 28	30-Day Safety Follow-up							
		Cycle 1 Day 1 (Baseline Visit)	Cycle 1 Day 2	Cycle 1 Day 3	Cycle 1 Day 4 (24 hrs post Day 3)	Cycle 1 Days 5 to 7	Cycle 1 Day 28													
Screening visit to occur within 21 days prior to first study drug administration. Cycle 1 Day 1 visit acts as the baseline visit																				
☐ INTERVIEWS & QUESTIONNAIRES																				
Subject information and Informed Consent	✓																			
Eligibility criteria	✓																			
Medical/oncological history	✓																			
ECOG Performance Status	✓	✓						✓			✓	✓								
Adverse event assessment	✓	✓	✓	✓	✓	✓	✓	✓	✓	✓	✓	✓								
Prior/concomitant therapy	✓	✓	✓	✓	✓	✓	✓	✓	✓	✓	✓	✓								
⌘ LABS & EXAMS																				
Height and Weight (Height at Screening only)	✓	✓						✓			✓									
Physical examination	✓	✓						✓			✓	✓								
A complete physical examination will be performed at Screening. A targeted physical examination will be performed at all other specified visits. A symptom-directed physical examination may be performed, as needed.																				
Vital signs	✓	✓	✓	✓	✓	✓	✓	✓	✓	✓	✓	✓								
12-lead electrocardiogram	✓																			
Serum pregnancy test	✓																			
Urine pregnancy test, if applicable			✓																	

Activity	Screening	Cycle 1							Cycle 2 Day 1, and Day 1 of every cycle thereafter	Cycles 2 to 6 Days 2 to 7	Cycle 2 Day 28 (only if CR/CRI not achieved at end of Cycle 1)	Cycle 4 Day 28 (only if CR/CRI not achieved at end of Cycle 2)	Final Visit/Cycle 6 Day 28	30-Day Safety Follow-up
		Cycle 1 Day 1 (Baseline Visit)	Cycle 1 Day 2	Cycle 1 Day 3	Cycle 1 Day 4 (24 hrs post Day 3)	Cycle 1 Days 5 to 7	Cycle 1 Day 28							
Cytogenetic Assessment	✓													
Molecular subtypes testing	✓													
Bone marrow aspirate	✓							✓			✓	✓	✓	
Clinical chemistry, hematology, and coagulation	✓	✓						✓	✓		✓	✓	✓	✓
TLS risk assessment	✓	✓	✓	✓	✓	✓								
Laboratory monitoring for TLS		✓	✓	✓	✓	✓								
Laboratory monitoring for TLS to occur at pre-dose, 4 - 6 hrs post-dose, and 24 hrs post-dose after each dose escalation.														
Post-treatment safety follow-up														✓

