- Depending on Investigator's choice of azacitidine or decitabine at Cycle 1 Day 1 (as per institutional practice): Azacitidine (75 mg/m^2) SC or IV administered for 7 days beginning on Day 1 of each 28-day cycle. Decitabine (20 mg/m^2) IV administered for 5 days beginning on Day 1 of each 28-day cycle. The subject must remain on the assigned therapy for the duration of the study.

## CYCLE 1, 2\*, and 4^; DAY 28

	INTERVIEW	
 
Adverse event assessment
 
Prior/concomitant therapy
 

	EXAM	
 
Vital signs
 

	LAB	
 
Clinical chemistry, hematology, and coagulation
 
Bone marrow aspiratea
 

	TREATMENT	
 
Dosing with venetoclaxb
 

**NOTES:** \* Cycle 2 Day 28: only if CR/CRI is not achieved at the end of Cycle 1.

^ Cycle 4 Day 28: only if CR/CRI is not achieved at the end of Cycle 2.

- Bone marrow aspirate must be collected within  $\pm$  3 days of the Day 28 visit in Cycles 1, 2, and 4, and the samples must be assessed and resulted prior to study drug administration for the subsequent cycle.
- Venetoclax (400 mg) PO will be administered QD for each 28-day cycle, except Cycle 1, due to 3-day ramp-up. If on concomitant posaconazole, strong or moderate CYP3A inhibitors, or P-gp inhibitors, refer to the Protocol, Table 1, for dose modifications.

## CYCLE 2 to 6; DAY 1

 INTERVIEW	
 
Adverse event assessment
 
ECOG Performance statusa
 
	
 
Prior/concomitant therapy
 

 EXAM	
 
Vital signsa
 
Physical examinationa,b
 
	
 
Weighta
 

 LAB	
 
Clinical chemistry, hematology, and coagulationa,c
 
	
 TREATMENT	
 
Collect venetoclax and subject diary
 
Dispense venetoclax and subject diary
 
	
 
Dosing with venetoclaxd
 
Dosing with azacitidine or decitabinee
 

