## 3.15 Bone Marrow Aspirate and/or Biopsy

---

Bone marrow aspirate will be performed at time points described in Section 2.1. Bone marrow aspirates performed throughout the study should be captured on an eCRF, including those performed to confirm or rule out disease progression. Bone marrow will be assessed at:

- Screening
- the end of Cycle 1 (must be performed within  $\pm 3$  days of Cycle 1 Day 28 and resulted prior to the administration of treatment for Cycle 2),
- the end of Cycle 2 (must be performed within  $\pm 3$  days of Cycle 2 Day 28 and resulted prior to administration of treatment for Cycle 3) [only if complete remission (CR)/complete remission with incomplete blood count recovery (CRI) not achieved at end of Cycle 1],
- the end of Cycle 4 (must be performed within  $\pm 3$  days of Cycle 4 Day 28 and resulted prior to administration of treatment for Cycle 5) [only if CR/CRI not achieved at end of Cycle 2], and
- upon concern for relapse, and

- the Final Visit/end of Cycle 6 (must be performed within  $\pm$  3 days of Cycle 6 Day 28).

Historical bone marrow aspirates and biopsies assessed locally to confirm the diagnosis can be used as baseline assessments to satisfy eligibility criteria and for screening as long as the samples were taken 30 days prior to first study drug administration. Bone marrow aspirates and/or biopsies performed in addition to those required per protocol, as standard of care throughout the study as per institutional practice, should also be captured on an eCRF.

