### 3.19 Unscheduled Visits

[figure not shown]
An Unscheduled Visit should be performed when the subject comes in for a medical visit for evaluation and assessment. During Unscheduled Visits, blood and urine samples may be obtained for the laboratory tests listed in Section 3, or for other tests, as determined by the investigator.

Visits for dispensing new study drug in case of temperature excursion, loss or damage are not considered an Unscheduled Visit. In addition, visits to only retest a lab will not be considered an Unscheduled Visit.

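### Scheduled blood counts are too far apart to verify the 7-day and 5-day conditions in SAP 9.4, and the SAP has no rule for the gaps between counts

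*SAP*

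**What the plan says.** **Endpoint.** Protocol 3.5 and SAP 4.3.3 list time to, and duration of, blood-count improvement as exploratory endpoints. In SAP 9.4 a Grade 4 neutropenia qualifies if it is "lasting for at least 7 days: when ANC lab values improve to $\geq 0.5 \times 10^9/L$ sustaining for a minimum of 5 days". Platelets and hemoglobin have rules of the same form. SAP 9.4.1 and 9.4.2 limit the analysis to subjects with blast clearance (CR, CRi or MLFS) and count days between dated laboratory values. SAP 9.4 applies Kaplan-Meier, with medians and 95% intervals. Nothing is said about an event known only to lie between two counts.

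**Scheduled counts.** In the Appendix H activity table, the row "Clinical chemistry, hematology, and coagulation" is ticked at Screening, Cycle 1 Day 1, Cycle 1 Day 28, Day 1 of Cycles 2 to 6, the Final Visit and the 30-day follow-up. It is also ticked at Cycle 2 Day 28 and Cycle 4 Day 28, but only for subjects not in CR/CRi at the end of Cycle 1 or Cycle 2 respectively. The visit lists in Operations Manual 2.1 and 2.2 agree. The ramp-up laboratory tests are a chemistry panel without a blood count (Operations Manual 3.14, Table 1). The visits on Days 2 to 7 of later cycles have no laboratory tests.

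**Counts outside the schedule.** Protocol 6.1 states: "Subjects will be monitored for blood counts through resolution of cytopenias". Protocol 6.2 holds treatment after CRi or MLFS at the end of Cycle 1 until ANC recovers, or for up to 14 days. For azacitidine, it asks for counts every 7 days when recovery is not seen by Day 28. Appendix G asks for monitoring during cycle delays. Operations Manual 3.14 covers follow-up of clinically significant out-of-range values.

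**Data capture.** Operations Manual 3.15 says that marrows done "as standard of care throughout the study as per institutional practice, should also be captured on an eCRF". Neither 3.14 nor 3.19 has a matching sentence for blood counts, and 3.19 adds that "visits to only retest a lab will not be considered an Unscheduled Visit".

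**The concern.** The endpoint needs a resolution of about a week, and the visit schedule gives about four weeks. If the analysis rests on scheduled counts, the medians would describe when visits took place rather than when marrow function recovered, and short mid-cycle episodes would leave no trace. SAP 10.3.2 takes the maximum post-baseline grade from collected values, so the shift tables could understate Grade 4 results.

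If the analysis uses whatever extra counts reach the database, their density may differ by site, by how ill the subject is, and by hypomethylating agent, because the only stated frequency (every 7 days) applies to azacitidine. SAP 5.2 reports results separately for the azacitidine and decitabine groups, so such a difference could look like a difference in recovery.

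**Working it through.** The documents give no precision or power figure for this analysis, so there is none to reproduce.

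**1. Calendar.** Take a subject in remission at the end of Cycle 1, with no delays. Day 1 of cycle k is study day 28(k − 1) + 1, which gives 1, 29, 57, 85, 113 and 141. Add Cycle 1 Day 28 (28), Cycle 6 Day 28 (168) and the 30-day visit (198).

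- Count days: 1, 28, 29, 57, 85, 113, 141, 168, 198.
- Gaps: 27, 1, 28, 28, 28, 28, 27, 30 days.

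**2. The two conditions.** Consecutive scheduled counts are 1 day apart or at least 27 days apart. A 1-day pair is too short to show 7 days low or 5 days recovered. A pair 27 or more days apart is compatible with either condition but does not show what happened in between.

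**3. Detection of an episode that begins after blast clearance.** Assume 28-day spacing, onset uniform within the interval, a true episode length of L days (L < 28) and no extra counts. Then P(seen) = L/28. The recorded time runs from the count that shows the drop to the next one, about 28 days, so it is too long by 28 − L.

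| L (days) | P(seen) = L/28 | Recorded time | Excess, 28 − L |
|---|---|---|---|
| 7 | 25% | about 28 | 21 |
| 10 | 36% | about 28 | 18 |
| 14 | 50% | about 28 | 14 |
| 21 | 75% | about 28 | 7 |

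**4. The same check on the actual calendar.** Require the episode to fall between Day 29 and the end of Day 168, so the onset window is 140 − L days. The counts on Days 57, 85, 113 and 141 each catch L days of onsets, and the Day 168 count catches one day. P(seen) = (4L + 1)/(140 − L).

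- L = 7: 29/133 = 22%
- L = 10: 41/130 = 32%
- L = 14: 57/126 = 45%
- L = 21: 85/119 = 71%

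These are slightly below the values in step 3 because late onsets are excluded. The recorded time is 27, 28 or 30 days, depending on which gap follows. No episode of up to 21 days gives two low counts at least 7 days apart. At 28 days about 1% do, and at 35 days about 21%. With the conditional Day 28 counts added for a subject not in remission, the shares seen hardly change: 23% at 7 days and 47% at 14 days.

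**5. Duration of improvement (SAP 9.4.2).** The end of the duration is a new drop below the threshold, which is detected with the same probabilities. A missed drop lengthens the recorded duration by at least one further cycle, and a detected one is dated only to within about 28 days.

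**6. Where this does not apply.** For neutropenia present at blast clearance after Cycle 1, SAP 9.4.1.1.1 runs from blast clearance to the first recovered ANC. Protocol 6.2 delays Cycle 2 for ANC recovery, and Operations Manual 2.1 requires the Day 1 count before dosing, so that count moves with recovery. The delay is driven by ANC, so platelets and hemoglobin do not benefit in the same way.

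**7. Why a rule is still needed with denser data.** With weekly counts added, every episode of 7 days or more is seen. Two low values at least 7 days apart are then available for all 14-day episodes, but for only about 42% of 10-day ones.

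**The case against.** The strongest reply is that the visit table is not the whole monitoring plan. Protocol 6.1, 6.2 and Appendix G and Operations Manual 3.14 call for counts while a cytopenia lasts, and the SAP definitions refer to laboratory values without limiting them to scheduled visits. That stands. A reader might infer from the schedule that these endpoints cannot be measured at all; the documents do not support this. What remains is that only the azacitidine rule gives a frequency, and that no supplied text says these counts enter the database.

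Three other stronger readings also go too far.

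- **That Operations Manual 3.19 keeps retest results out of the data.** It only classifies visits, and says nothing about recording the result. eCRF completion instructions, which are not among the documents, may already require it. The point is silence, in contrast with the express rule for marrows in 3.15.
- **That every episode is recorded as 28 days.** This holds only for detected later-onset episodes shorter than the gap, with no extra counts. It does not hold for neutropenia present at blast clearance after Cycle 1.
- **That the secondary objective on neutropenia is undermined.** That objective concerns adverse events. SAP 10.2.1 and 10.2.3 address it mainly through adverse-event summaries, including a dedicated neutropenia search. Adverse events are assessed on Days 2 to 7 of later cycles even though no laboratory tests are scheduled. Only the shift tables depend on collected counts.

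It is also fair to say that these are descriptive endpoints in a single-arm study of about 60 subjects, with no test or decision attached. That limits how much the point matters. It does not make ordinary Kaplan-Meier suitable for dates known only to within about four weeks.

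**Conclusion.** The concern holds for scheduled counts. They cannot verify the 7-day and 5-day conditions. For later-onset cytopenias and for duration of improvement, the planned Kaplan-Meier times would largely reflect visit spacing. Under the stated assumptions (28-day spacing, uniform onset, no extra counts), between 25% of 7-day episodes and 75% of 21-day episodes are seen, and the recorded time is too long by about 21 and 7 days respectively. The episode lengths are illustrative, because the documents give none.

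Event-driven counts will reduce these errors by an amount that cannot be worked out from the documents, and unevenly if their density varies. The maximum-grade shift tables may understate mid-cycle Grade 4 values. The primary endpoint and transfusion independence do not use the 7-day and 5-day rules. The change is worth making because it is cheap, not because a main conclusion depends on it.

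**What to change.** **Operations Manual 3.14 and 3.19.** Require every local blood count taken from Cycle 1 Day 1 to the 30-day visit, including those from retest-only visits, to be entered in the eCRF with its date, as 3.15 already does for extra marrows.

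**SAP 9.4.**

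- Analyse time to, and duration of, improvement as interval-censored between the last value on one side of the threshold and the first on the other, for example with the Turnbull estimator. Where the start is also known only to an interval, use the shortest and longest times compatible with the counts as bounds, and say that this is an approximation.
- State how the 7-day and 5-day conditions are judged when adjacent counts are further apart than that.
- Report the gaps between counts, overall and by hypomethylating agent, and the number of subjects whose episodes cannot be verified. Interval censoring does not recover an episode that was never sampled, so this table is needed to read the results.
- Do not restrict the main analysis to episodes with closely spaced counts. That would select the more intensively monitored subjects.

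**Cost.** Operations Manual and SAP wording, site time to enter results already in the local chart, and somewhat wider intervals. No extra blood draw is needed.

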9.4.1 Time to Blood Count Improvement

Time to blood count improvement will be analyzed for subjects who achieved bone marrow blast clearance (CR/CRi/MLFS).

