## 3.5 Exploratory Research and Validation Endpoints

---

The exploratory endpoints are to:

- Evaluate the time to blood count improvements and duration of blood count improvements for subjects who experience cytopenias and anemia.
- Evaluate effectiveness (CR/CRI) in molecular subtypes identified per institutional practices.

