4.3.3 Exploratory Efficacy Endpoints

The exploratory endpoints are:

- Time to the first improvement of absolute neutrophil count (ANC), platelets, and hemoglobin as well as duration of the first improvement of absolute neutrophil count, platelets and hemoglobin. See Section 9.4.1 for definitions of both endpoints.
- Rates of CR/CRI in molecular subtypes identified per institutional practices.

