5.0 Analysis Populations

5.1 Definition of Analysis Populations

Subjects who receive at least one dose of venetoclax, azacitidine, or decitabine will be included in all analyses unless specified otherwise.

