9.4.1.1 Time to Improvement of Grade 4 Neutropenia

9.4.1.1.1 Time to Improvement of Grade 4 Neutropenia Present at the Time of Blast Clearance

For subjects whose ANC lab value is $<0.5 \times 10^9/L$ at the time of blast clearance, their time to improvement of Grade 4 neutropenia present at the time of blast clearance is defined as number of days from the blast clearance to the first date of ANC lab value recovered to $\geq 0.5 \times 10^9/L$.

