9.4.2 Duration of Blood Count Improvement

Duration of blood count improvement will be analyzed for subjects who achieved bone marrow blast clearance (CR/CRi/MLFS).

9.4.2.1 Duration of Improvement of Grade 4 Neutropenia Present at the Time of Blast Clearance

For subjects whose ANC lab value is $<0.5 \times 10^9/L$ at the time of blast clearance with a subsequent improvement, the duration of improvement of Grade 4 Neutropenia present at the time of blast clearance is defined as number of days from the first date of ANC lab value recovered to $\geq 0.5 \times 10^9/L$ following blast clearance to the first date when ANC lab value dropped back to $<0.5 \times 10^9/L$.

9.4.2.2 Duration of Improvement of Grade 4 Thrombocytopenia Present at the Time of Blast Clearance

Analyses will be performed similar to Duration of Improvement of Grade 4 Neutropenia.

9.4.2.3 Duration of Improvement of Grade 3 Anemia Present at the Time of Blast Clearance

Analyses will be performed similar to Duration of Improvement of Grade 4 Neutropenia.

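### The SAP analyses blood count improvement only in subjects with blast clearance, from clearance onward, so the protocol's question about all subjects with cytopenia has no analysis

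*SAP*

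**What the plan says.** Protocol 3.5 states the exploratory aim as: "Evaluate the time to blood count improvements and duration of blood count improvements for subjects who experience cytopenias and anemia". Nothing there depends on marrow response. SAP 4.3.3 names "Time to the first improvement of absolute neutrophil count (ANC), platelets, and hemoglobin", together with the duration of that improvement. It also states no restriction, but adds: "See Section 9.4.1 for definitions of both endpoints".

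The restriction appears in SAP 9.4.1, "Time to blood count improvement will be analyzed for subjects who achieved bone marrow blast clearance (CR/CRi/MLFS", and again in SAP 9.4.2, "Duration of blood count improvement will be analyzed for subjects who achieved bone marrow blast clearance (CR/CRi/MLFS". SAP 9.4.1.1.1 covers neutropenia present at clearance and measures the "number of days from the blast clearance to the first date of ANC lab value recovered" to the threshold. SAP 9.4.1.1.2 covers the first drop below the threshold after clearance and measures from that drop. Platelets and hemoglobin follow the same pattern. SAP 9.4.2.1 to 9.4.2.3 define duration only for a cytopenia present at clearance.

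The general rule in SAP 5.1 is: "Subjects who receive at least one dose of venetoclax, azacitidine, or decitabine will be included in all analyses unless specified otherwise". Section 9.4 is therefore an explicit exception to the all-treated set. No reason is given, and neither an all-subject analysis nor a count of those left out is planned.

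**The concern.** Blast clearance is observed after treatment starts and is closely tied to count recovery. Selecting on it changes who is studied, and starting the clock at or after it changes what is timed. A Kaplan-Meier median from SAP 9.4 tells a site how long counts take to recover once the marrow has cleared. It does not tell the site how often, or how soon, a treated outpatient with a cytopenia recovers, which is what Protocol 3.5 asks. If the result is reported under the protocol's endpoint name without qualification, the two could be confused.

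**Working it through.** **No planned figure exists for this endpoint.** The only design figure is the precision of the CR + CRi rate, within 13% with 60 subjects (SAP 4.4). It reproduces: 1.96 × √(0.5 × 0.5 / 60) = 0.1265, or about 13 points. It does not bear on blood counts.

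**Which cytopenias are analysed.** Reading SAP 9.4.1 and 9.4.2 case by case:

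| Cytopenia | Time to improvement | Duration |
|---|---|---|
| Subject never clears blasts (PR, resistant, progressive, no marrow result) | not analysed | not analysed |
| Starts and resolves before clearance | not analysed | not analysed |
| Present at clearance | from clearance, not from onset | analysed |
| Starts after clearance | from the first drop | not analysed |

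Under Protocol 3.5 all four rows belong to the endpoint. In the second row, the first improvement named in SAP 4.3.3 is not the one measured. This step needs no assumption.

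**How many subjects cannot enter.** Inputs: N = 60; expected CR + CRi of about 60% (Protocol 2.1, clinical hypothesis); 70% with azacitidine and 74% with decitabine in the earlier combination study (Protocol 2.1). Number without CR or CRi = 60 × (1 − rate):

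- 60%: 60 × 0.40 = 24
- 70%: 60 × 0.30 = 18
- 74%: 60 × 0.26 = 15.6, about 16

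At each rate these are upper bounds on the cytopenic subjects left out, because MLFS also counts as clearance and not every subject will have a cytopenia meeting the SAP 9.4 definition.

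**What the selection could do to a recovery proportion.** Let c be the share cleared among cytopenic subjects, rc recovery if cleared and rn recovery if not. Recovery in all = c·rc + (1 − c)·rn, so the gap is (1 − c)(rc − rn). The documents give neither rc nor rn. Assume rc = 80% and vary rn:

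| rn | All subjects, c = 0.60 | Gap | All subjects, c = 0.70 | Gap |
|---|---|---|---|---|
| 0% | 48% | 32 points | 56% | 24 points |
| 30% | 60% | 20 | 65% | 15 |
| 50% | 68% | 12 | 71% | 9 |
| 80% | 80% | 0 | 80% | 0 |
| 100% | 88% | −8 | 86% | −6 |

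**And to a median.** Assume exponential recovery with a 14-day median in cleared subjects, c = 0.60, and the same clock for everyone, so that only selection acts. If the recovery hazard in non-cleared subjects is 0, 0.2, 0.5, 1 or 2 times that of cleared subjects, the all-subject median is 36, 24, 18, 14 or 10 days.

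**What the documents say about direction.** In Protocol 6.2 (Management of Cytopenias), after CRi or MLFS venetoclax is interrupted, and azacitidine or decitabine delayed, for ANC to reach 500/µL. Subjects with resistant disease are treated without interruption until CRi or MLFS. Appendix G says that before remission cycles should mostly not be interrupted for cytopenias. An ANC of 500/µL is also the SAP 9.4 improvement threshold (0.5 × 10⁹/L). This favours better recovery in the analysed set. Pulling the other way, PR requires all the blood values of a CR (Operations Manual, Table 2) yet lies outside the cleared set, and quick recoveries before clearance are also lost.

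**The case against.** The strongest defence is that blast clearance is the point at which the protocol's own handling of cytopenias changes. Recovery after clearance separates treatment-related cytopenia from disease-related marrow failure. Because the clock starts at or after clearance, there is no immortal time. The SAP states the condition openly, the subsection titles repeat it, SAP 5.1 allows exceptions, and Protocol 7.3 leaves analysis detail to the SAP. The endpoint is exploratory and untested. All of this stands, and it is why the current analysis should be kept. It does not supply an analysis for the population named in Protocol 3.5.

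Three stronger readings are tempting and are not supported:

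- A reader might infer that recovery is overstated as a matter of fact. The sign depends on non-cleared subjects recovering less or later. That is plausible, but the documents give no figure, and the tables above show that it can vanish or reverse. Calling the excluded group non-responders is also loose: MLFS is kept and PR is dropped.
- A reader might infer that a subject in CR can never have neutropenia present at clearance. Operations Manual 3.16 lets counts from up to 2 weeks after the marrow determine response when treatment is delayed for count recovery. Such a subject could be below the threshold on the marrow date. CR also has no hemoglobin threshold.
- A reader might infer that most early episodes are lost because of the SAP. Scheduled Cycle 1 hematology falls on Days 1 and 28, and the Day 2 to 7 draws are TLS chemistry. Many short episodes would be missed under any analysis that relies on scheduled counts. Protocol 6.1 has counts monitored through resolution of cytopenias but gives no frequency.

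**Conclusion.** The mismatch is established from the text alone: the SAP changes both the population and the time origin of a protocol endpoint, and leaves later-onset cytopenia without a duration analysis. It is a different estimand, not an error within its own terms. The exclusion could reach 24 of 60 treated subjects at 60% remission, taking CR + CRi as the lower limit for clearance. A more favourable picture than in all cytopenic subjects is likely, given how dosing is handled before and after clearance, but its direction and size remain unproven; the illustrations rest on assumed recovery rates. Primary and secondary results are unaffected, so this is a low-priority point that is still worth making.

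**What to change.** Keep the analyses in SAP 9.4.1 and 9.4.2. Label them in the SAP and in the outputs as conditional on blast clearance, and report how many subjects with a qualifying cytopenia are left out.

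Add beside them an analysis of all treated subjects who meet the SAP 9.4 cytopenia definition, whatever their marrow response. Time runs from the first qualifying value (from first dose if the cytopenia is present at baseline) to first improvement. Present it as cumulative incidence, with death or start of new anti-leukaemia therapy as competing events. Because 9.4.2 carries the same restriction, summarise duration from that first improvement in this set.

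In the existing clearance-based set, add duration of improvement for cytopenias that start after clearance.

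The cost is SAP text and a few tables from data already collected. The limitation is coarse dating: with sparse scheduled hematology in Cycle 1, onset and recovery dates, and the 7-day requirement in SAP 9.4, will be known only approximately, and the report should say so. Making the all-subject analysis the main one in place of the current one is a matter of preference and is not needed.
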